Sample size: Teare et al., 2014 recommended that a pilot study is required a total number of participants between 60 and 100 when estimating the effect size for a continuous outcome. Thus, sixty participants will be recruited from six community centres. We estimate that about 25-50% of the members of these centres will be eligible to participate (Schultz-Larsen et al., 2007; Liu, 2017). We will target moderate to large centres with the total number of centre members around 800. Given that we can screen 200 older people (50 in each centre) per 4 to 6 weeks, and based on our previous study in similar centres (Liu et al., 2017), we believe that we will need about 3 to 4 months to recruit 60 participants (with 30 subjects recruited per 4 to 6 weeks in two-three centres) for this study. Given the difficulty of obtaining details of the backgrounds of all potential participants in these community settings, a properly random sample cannot be implemented. Thus, convenience sampling will be used to recruit participants among the collaborative community centres. Using computer-generated random numbers, a biostatistician not affiliated with this study will randomize the centres in a 1:1 ratio into either: the control or the experimental groups. Participants from each centre will be placed in their centre's corresponding group to avoid 'contamination' effects across participants. To avoid selection biases, the allocation to the study groups will be concealed from the researchers until sample recruitment and baseline measurements have been completed. Appendices 1 and 2 show the CONSORT research flow chart and the timeline of this study.

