The Control Condition: The same physical training and BCTs support will be arranged for the control group.

Instruments and Measures:

Participants will be assessed on a variety of outcomes (described below) at 1 week and at 1 and 3 months (T1 – T3) after the programme, which will be compared with the baseline assessment (T0). The participants will be asked to wear an ActiGraph Wgt3x accelerometer on their non-dominant wrist for 7 days before the commencement of any intervention, as well as during each outcome assessment time point.

Socio-demographic data: The following data will be collected: 1) data on age, gender, marital status, exercise habits, living conditions, and level of education, 2) the participants' health-related information, including their morbidities, cognitive status, medications, and number of hospital and out-patient clinic visits in the past 12 months.

Feasibility:

To understand the feasibility of this intervention, the frequency with which the participants in the experimental group use the tracker over the time of the study (i.e., 112 days), the recruitment rate, the attrition rate, the participants' adherence to the exercise regimen, and reports of adverse effects will be monitored.

Primary outcome measurement: Activity levels

The participants' physical activities and sedentary time will be objectively measured using a ActiGraph wGT3X accelerometer.

Secondary outcome measurements

Fitbit Data (only participants in the experimental group): The total steps per week, total walking distance per week, and time spent in different heart rate zones (50-69%, 70-84%, and >85% of the maximum heart rate) of an individual will be collected.

Physical Endurance: This will be evaluated using different physical tests:

1. The participants' lower-limb muscle and upper-limb strength will be assessed using a 30-second chair stand test and a handheld Jamar Hydraulic Hand Dynamometer, respectively.
2. Mobility will be assessed through the Timed-up-and-Go (TUG) test and by their gait speed (2-m walk). These two tests assess the overall performance of the lower limbs and walking speed, which can reflect the effect of exercise in enhancing the participants' overall physical endurance.

Exercise Self-efficacy: The participants' self-confidence in their ability to exercise in a variety of circumstances (e.g., even when they were feeling tired) will be assessed using the Chinese Self-Efficacy for Exercise scale (CSEE).

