Frailty status: This will be assessed based on Fried's frailty five phenotypes as mentioned in the sample inclusion criteria. **Physical activity level** is one criterion of frailty that will be assessed using the 10-item PASE-C to measure self-reported occupational, household, and leisure activities for the last week.

Self-reported sedentary behavioral and physical activity: This will be assessed using the Global Physical Activity Questionnaire-Chinese version (C-GPAQ), which comprises 16 questions designed to estimate an individual's self-perceived level of physical activity in three domains (occupational, transport-related and discretionary or leisure time).

Motivation to engage in physical activity: This will be assessed by the 19-item Chinese version of the Behavioral Regulation in Exercise Questionnaire-2 (C-BREQ-2). The C-BREQ-2 is a 19-item questionnaire assessing five dimensions: amotivation, external regulation, introjected regulation, identified regulation, and intrinsic regulation. Each item is rated on a 5-point scale ranging from 0 = "not true for me" to 4 = "very true for me", with higher scores indicative of higher motivation.

Procedures: Ethical and access approval will be obtained from the Ethics Review Committee of The University and study venues, respectively. Potential participants will be referred to the research team by the community centres. An RA will screen all potential participants for their eligibility to participate in this study. Written informed consent will then be obtained from all of the participants, to whom all aspects of the study will be explained and questions answered. They will then be interviewed to obtain their demographic data, and baseline assessment. After that, the participating community centres will be randomized to either the control or experimental group. Participants from each centre will be placed into their centre's corresponding group to avoid 'contamination' effects across participants. At 1 week, 1 month, and 3 months post-intervention, an independent assessor who is blinded to the group allocations will assess the participants' outcomes, which will be compared with the baseline assessment. Another RA will collect all "Fitbit activity-related data" from the participants in the experimental group every week. All of the participants in the experimental group will be invited to attend the focus group interviews, which will be conducted by JS after the first post-test T1 and T3.

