Official Title: Enhancing physical activity levels of community-dwelling older people with frailty through an exercise intervention with or without a wearable activity tracker (WAT)-based intervention: a feasibility and pilot study

Date of the document: 22/03/2018

Approved by the Human Subjects Ethics Sub-committee of The Hong Kong Polytechnic University on 13/04/2018

Statistical Analysis:

SPSS version 23.0 will be used to analyse the data. Descriptive statistics will be generated for the demographic data and feasibility tests. The baseline characteristics of the participants in the two groups from the six community centres will be compared using unpaired t test for the continuous variables, a chi-square test for the categorical variables, and the Mann-Whitney U test for the ordinal variables. Normality assumptions for the variables will be examined by a K-S test. The group attendance and drop-out rate of the participants in the study groups will be reported. An intention-to-treat analysis will be adopted. An independent sample Student's t-test or Mann-Whitney U test will be used to examine differences between the control and experimental groups in the outcome variables. For categorical and dichotomous outcome variables, an χ^2 test will be used to test differences between the groups. If significant differences between the groups at baseline have been identified, these data will be treated as covariates and adjusted for as needed. A p-value of < 0.05 will be considered statistically significant. ANOVA will be used to measure the effectiveness of the intervention. If the data were non-normal, Friedman's test will be used instead. Post-hoc within-group comparisons will be done using paired t-tests or Wilcoxon's signed rank test, and Bonferroni adjustments will be made.

Content analysis will be used to analyse the interview data. All audio-taped interviews will be transcribed into Cantonese by the RA and the transcriptions will be checked for accuracy by two members of the research team before the analysis.

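### Baseline is to be completed before the six centres are randomised, but the draw does not use it, and the SAP adjusts for baseline only after a significant test

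*Protocol*

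**What the plan says.** **Order of events.** The Procedures section of the Protocol takes consent, demographic data and the baseline assessment first, then states: "After that, the participating community centres will be randomized to either the control or experimental group". The Sample size section agrees: "the allocation to the study groups will be concealed from the researchers until sample recruitment and baseline measurements have been completed".

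**The draw.** The same section says "sixty participants will be recruited from six community centres", and describes the allocation as follows: "Using computer-generated random numbers, a biostatistician not affiliated with this study will randomize the centres in a 1:1 ratio into either" of the two groups. Neither document names stratification, matching, minimisation or any other constraint.

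**Timing details.** Recruitment runs in waves, "with 30 subjects recruited per 4 to 6 weeks in two-three centres", over about 3 to 4 months. Under Instruments and Measures, the baseline accelerometer is worn "for 7 days before the commencement of any intervention". That ties it to the start of intervention and not to the date of the draw.

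**Analysis.** The SAP compares the arms at baseline and then says: "If significant differences between the groups at baseline have been identified, these data will be treated as covariates and adjusted for as needed".

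**The concern.** Many cluster trials randomise before participants are known. This plan measures baseline first, so the independent biostatistician could see coded centre summaries before drawing. With only six centres, an unconstrained 3 v 3 split can leave the arms well apart on a variable that predicts the outcome, above all baseline activity, which is the T0 value of the primary outcome.

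The Sample size section justifies 60 participants by the aim of estimating an effect size for a continuous outcome, and the Background says the result will lead to a larger main study. A baseline gap left in the comparison can distort that estimate. Let *r* be the correlation between baseline and follow-up in SD units. A comparison of follow-up values then carries about *r* × gap, and a comparison of changes carries about −(1 − *r*) × gap. The SAP plans between-arm tests and an ANOVA without saying whether T0 is in the model, so either could apply.

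**Working it through.** **Inputs from the documents:** six centres, 60 participants, 1:1 allocation of centres (3 v 3), significance level 0.05.

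**Assumptions:** equal centres of 60/6 = 10; two-sided baseline test (sidedness is not stated); ICC from 0 to 0.10, with 0.05 as the working value (none is given).

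**The plan's own figure.** The 60 comes from a cited rule of 60 to 100 participants for pilots, not from a power formula. Beyond 6 × 10 = 60 there is nothing to reproduce, and the plan states no imbalance probability.

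**Step 1: chance imbalance on one variable.** In SD units, the arm gap has standard error SE = √[(2/30) × (1 + 9 × ICC)], and P(|gap| > c) = 2 × [1 − Φ(c/SE)]. At ICC 0.05, SE = √(0.0667 × 1.45) = 0.311. Then 0.5/0.311 = 1.61 gives 10.8%, and 0.3/0.311 = 0.965 gives 33%.

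**Step 2: the SAP's trigger.** With 30 per arm, the baseline t-test is significant at a gap of t(0.975, 58 df) × √(2/30) = 2.002 × 0.258 = 0.517 SD.

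| ICC (assumed) | SE | gap > 0.5 SD | gap > 0.3 SD | gap > 0.517 SD | gap 0.3 to 0.517 SD |
|---|---|---|---|---|---|
| 0 | 0.258 | 5.3% | 25% | 4.5% | 20% |
| 0.01 | 0.270 | 6.4% | 27% | 5.5% | 21% |
| 0.05 | 0.311 | 10.8% | 33% | 9.6% | 24% |
| 0.10 | 0.356 | 16.0% | 40% | 14.6% | 25% |

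The last column is the difference of the two before it: the share of trials with a sizeable gap and no adjustment triggered. With unequal centres of 5 to 15 at ICC 0.05, the chance above 0.5 SD is 11.7%.

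**Step 3: what a constrained draw does.** There are C(6,3) = 20 allocations. Each has a mirror image with the same absolute gap, so the best 10 are only 5 distinct splits. A given pair of centres is together in 2 × 4 = 8 of the 20 and apart in 12. A set of 10 therefore cannot keep a pair always together, but it can keep one always apart. In simulation this happened in about 63% of trials when balancing on one variable and 53% on three. A set of 14 exceeds 12, so it can never do so. Widening from 10 to 12 and then 14 always ends.

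Simulated results at ICC 0.05, with that widening rule:
- One balancing variable: gap above 0.5 SD falls from 11% to about 0.4%; above 0.3 SD, from 33% to about 8%.
- Three independent balancing variables: at least one gap above 0.5 SD falls from 29% to about 6%.

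**Step 4: permutation reference set.** The smallest two-sided p is 2/20 = 0.10 for the unconstrained draw, and 2/10 = 0.20, 2/12 = 0.17 or 2/14 = 0.14 for the constrained one.

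**The case against.** The plan's draw is valid and unbiased, and this is a feasibility pilot. The SAP does not ignore imbalance: its trigger of 0.52 SD nearly coincides with a 0.5 SD gap, so most gaps that large would be adjusted for. Outcomes are also to be compared with T0. All of this stands. What remains is the band below the trigger, and the weakness of a test-driven, discretionary rule beside adjustment fixed in advance.

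Feasibility is a fair challenge too. Centres are recruited in waves and accelerometer wear is tied to the start of intervention, so the documents do not establish that scored accelerometer data from all six centres would exist at one moment. The two sections on order of events read most naturally that way, but the plan must say so.

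A reader might infer three stronger points that the documents do not support:
- *One trial in ten starts badly unbalanced.* That needs an ICC near 0.05, which is assumed, and it applies to one variable at a time.
- *Prevention is free and complete.* It needs earlier scoring and one closing date, it shrinks the permutation set, and it is incomplete when several variables are balanced.
- *Later adjustment is impossible with six centres.* The limit of 6 − 2 = 4 between-centre degrees of freedom concerns centre-level covariates. Adjustment for each participant's own baseline value remains available.

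**Conclusion.** The point holds as a worthwhile design improvement. The plan is set to have baseline data before it randomises, does not use them in the draw, and leaves baseline adjustment to a significance test. For ICC 0 to 0.10 and 10 per centre, the chance of a gap on one given variable is 5% to 16% above 0.5 SD and 25% to 40% above 0.3 SD. At ICC 0.05, about 24% of trials would have a gap of 0.3 to 0.52 SD with no covariate adjustment triggered. These figures rest on the assumed ICC, equal centre sizes and approximate normality of centre means. They do not show that the randomisation is biased or that any number in the plan is wrong.

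**What to change.** **1. Protocol, Sample size (randomisation) and Procedures.** State that there is a single draw after T0, including scored accelerometer data, is closed in all six centres. Name the one accelerometer activity summary to be used. The independent biostatistician, working from coded centre summaries:
- lists the 20 allocations and ranks them by the absolute arm gap in mean baseline activity;
- keeps the best 10, widening to 12 and then 14 if any two centres are always together or always apart;
- draws one of those kept at random.

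Balancing on this variable alone gives it the tightest control. Adding more weakens the control on each.

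**2. SAP, Statistical Analysis.** Replace the significance trigger with prespecified adjustment for each participant's baseline accelerometer value in the primary outcome model.

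**Cost.** No extra participants or measurements. Accelerometer files must be scored before the draw. All six centres must finish T0 first, so centres in an early wave would wait and their baseline would be older when intervention starts; the accelerometer timing wording must be reconciled with this. The smallest two-sided permutation p rises from 0.10 to between 0.14 and 0.20, though the SAP plans no permutation test. If waiting for all six centres is not workable, part 2 can be adopted alone.

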Appendix 1: Consort Research Flowchart

Appendix 2: Example of lecture notes about tips of exercise safety

Example of lecture notes about tips of exercise safety

Centre for Gerontological Nursing 運動安全小貼士

戶外運動-
預防熱衰竭與中暑

空氣質素健康指數

Official Title: Enhancing physical activity levels of community-dwelling older people with frailty through an exercise intervention with or without a wearable activity tracker (WAT)-based intervention: a feasibility and pilot study

Date of the document: 22/03/2018

Approved by the Human Subjects Ethics Sub-committee of The Hong Kong Polytechnic University on 13/04/2018

Statistical Analysis:

SPSS version 23.0 will be used to analyse the data. Descriptive statistics will be generated for the demographic data and feasibility tests. The baseline characteristics of the participants in the two groups from the six community centres will be compared using unpaired t test for the continuous variables, a chi-square test for the categorical variables, and the Mann-Whitney U test for the ordinal variables. Normality assumptions for the variables will be examined by a K-S test. The group attendance and drop-out rate of the participants in the study groups will be reported. An intention-to-treat analysis will be adopted. An independent sample Student's t-test or Mann-Whitney U test will be used to examine differences between the control and experimental groups in the outcome variables. For categorical and dichotomous outcome variables, an χ^2 test will be used to test differences between the groups. If significant differences between the groups at baseline have been identified, these data will be treated as covariates and adjusted for as needed. A p-value of < 0.05 will be considered statistically significant. ANOVA will be used to measure the effectiveness of the intervention. If the data were non-normal, Friedman's test will be used instead. Post-hoc within-group comparisons will be done using paired t-tests or Wilcoxon's signed rank test, and Bonferroni adjustments will be made.

Content analysis will be used to analyse the interview data. All audio-taped interviews will be transcribed into Cantonese by the RA and the transcriptions will be checked for accuracy by two members of the research team before the analysis.

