Although the ultimate goal of using WATs should be increased MVPA, such data was not reported in previous studies on older people. Moreover, the suggested additional measures for facilitating the adoption of WATs by older people have not previously been tested. It is worth testing the efficacy of a combined intervention of exercise training plus WAT intervention in which BCTs have been incorporated. Little is presently known about the efficacy of using a WAT intervention among older people with frailty. The main hypothesis is that the WAT intervention plus exercise training programme will increase physical activity levels compared to an exercise programme alone. If we are successful in proving the hypothesis, we will propose studying the long-term effects (i.e., increased daily MVPA and the adoption of a physically active lifestyle) of this intervention in the main study with a larger sample size with a longer follow-up period.

B. Research plan and methodology (Appendix 1: Consort Research Flowchart)

Aim: A single-blinded, repeated-measures, two-arm pilot cluster RCT is proposed to examine the feasibility and preliminary effects of an exercise programme with or without a WAT intervention for promoting physical activity levels among community-dwelling older people with frailty. To explore the acceptability of the WAT intervention, a focus group with all participants in the experimental group (4-6 people per group) will be interviewed by JS (the Co-I).

Subjects and Settings: A district community health centre will be viewed as one unit/cluster. Eligibility criteria for district community health centres are those that are funded by the Hong Kong (HK) government and under the supervision of the Social and Welfare Department of HK, and thus that meet a specific set of standard regulations and criteria on environment and practices. Six community centres, which provide similar types of community care and social support services for community-dwelling older people, will be invited by a convenience method to work as collaborators in this study. The target population of this study are community-dwelling older people with frailty who will be recruited through the community centres.

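### The sample size is justified for estimating an effect size, but for the outcomes the SAP pre-specifies only significance tests: no between-arm estimate with interval, no SD and no centre ICC

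*SAP*

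**What the plan says.** **Purpose of the sample size.** The Protocol (section B, Sample size) rests the number on a cited recommendation that "a pilot study is required a total number of participants between 60 and 100 when estimating the effect size for a continuous outcome", and concludes that "sixty participants will be recruited from six community centres". A biostatistician "will randomize the centres in a 1:1 ratio into either: the control or the experimental groups".

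**Aim and next step.** Section B, Aim: "A single-blinded, repeated-measures, two-arm pilot cluster RCT is proposed to examine the feasibility and preliminary effects". The closing paragraph of section A says that, if the hypothesis is borne out, long-term effects will be studied "in the main study with a larger sample size with a longer follow-up period".

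**Primary outcome.** Section B, Instruments and Measures: "The participants' physical activities and sedentary time will be objectively measured using a ActiGraph wGT3X accelerometer".

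**Planned analysis.** The SAP (Statistical Analysis) says "Descriptive statistics will be generated for the demographic data and feasibility tests" and adds attendance and drop-out by group. For the outcomes it lists t or Mann-Whitney tests, chi-square tests, ANOVA with Friedman's test as the non-normal alternative, and paired t or Wilcoxon tests within groups with Bonferroni adjustment, judged at 0.05. The only intra-class correlation in either document is in the Protocol's paragraph on intervention fidelity and RA training, and it concerns rater reliability.

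**The concern.** The one reason given for 60 participants is estimation, yet the analysis plan for the outcomes names no quantity to be estimated. For a trial intended to lead to a larger one, the useful results are the size of the difference, how precisely it is known, the spread of the outcome, and how strongly measurements within a centre resemble each other. A list of p-values from six centres conveys none of these. A non-significant result could be read as no effect, and a significant one as an effect of known size, when the data are compatible with a wide range of differences. This is a separate question from whether the listed tests are valid under cluster randomisation: a valid clustered test reported only as a p-value would leave the same gap.

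**Working it through.** **1. The stated sample size.** 60 / 6 = 10 per centre. Allocation of centres at 1:1 gives 3 centres and about 30 participants per arm. The figure of 60 is the lower end of the cited 60 to 100. It cannot be derived further, because the documents give no effect size, SD, power, target precision, centre ICC or dropout allowance.

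**2. What the plan commits to for the outcomes.**

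| Quantity | Named in the SAP? | Obtainable from the listed methods? |
|---|---|---|
| Between-arm difference | No | From the arm means behind a t-test or ANOVA. Mann-Whitney compares ranks, not means. Friedman's test ranks repeated measures within participants and has no arm comparison. |
| 95% CI that respects centres | No | No: no method has a centre term |
| Outcome SD | No | Yes, from the data, but reporting is not promised |
| T0-to-visit correlation | No | Yes, from the data, but reporting is not promised |
| Centre ICC | No | No: no method has a centre term |

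**3. How wide the unreported interval would be.** This illustration uses an unadjusted difference at one visit, in SD units, two-sided 95%, with equal centres and no dropout. The documents give no centre ICC, so 0.01, 0.05 and 0.10 are assumed.

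Ignoring centres (58 df): 2.00 × √(2/30) = 2.00 × 0.258 = 0.52 SD.

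Analysing at centre level (6 − 2 = 4 df): half-width = 2.776 × √[(2/3) × (ICC + (1 − ICC)/10)].

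- ICC 0.01: 2.776 × √(0.667 × 0.109) = 0.75 SD
- ICC 0.05: 2.776 × √(0.667 × 0.145) = 0.86 SD
- ICC 0.10: 2.776 × √(0.667 × 0.190) = 0.99 SD

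Much of the widening comes from having only 4 degrees of freedom. At ICC 0 the centre-level figure is already 0.72 SD.

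These are not the widths of the adjusted estimate recommended below. That width depends on the T0-to-visit correlation, which is unknown and is one of the quantities the pilot should report.

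**4. How well the SD and ICC could be estimated.**

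- SD, treating participants as independent (58 df): the 95% limits are 0.85 and 1.22 times the estimate.
- Centre ICC, if 0.05 were observed: F = (1 + 9 × 0.05)/(1 − 0.05) = 1.526 on 4 and 54 df. Lower limit: 1.526/3.03 = 0.503, so (0.503 − 1)/(0.503 + 9) = −0.05. Upper limit: 1.526 × 8.37 = 12.78, so (12.78 − 1)/(12.78 + 9) = 0.54.

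The SD is therefore fairly well determined, and the ICC hardly at all.

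**The case against.** Several counter-arguments have force.

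- **The estimates can be produced anyway.** A t-test is built from arm means and SDs, and the sentence on descriptive statistics does not say that outcomes are excluded. This stands. The fault is that the plan does not pre-specify the estimates, not that they are lost. It does not cover the centre-respecting interval or the ICC, which need an analysis that recognises centre.
- **Estimation is a clause in the sample-size paragraph, not the trial's aim.** True, and the main study is conditional on the hypothesis being supported, which fits a test. But the aim includes preliminary effects, and estimation is the only reason given for the number recruited.
- **Six centres cannot give a useful ICC.** Largely right, as step 4 shows. That argues for reporting it with its interval, for one outcome only, and against relying on the point value.

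Two stronger readings are tempting and are not supported. A reader might infer that the pilot yields nothing but p-values and none of the inputs for a main study. In fact recruitment, attrition, adherence, tracker use and adverse effects are to be monitored, attendance and drop-out are to be reported by group, and interviews are to be analysed. A reader might also infer that a main study planned without the ICC would be too small by 1 − 1/(1 + 9 × ICC), or 8%, 31% or 47% at ICC 0.01, 0.05 or 0.10. That assumes a cluster-randomised main study with 10 per centre and no ICC from elsewhere. The documents say only that it would be larger and longer, and six centres could not settle the ICC in any case.

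**Conclusion.** The concern holds as a mismatch between the reason for the sample size and the outcome analysis that is pre-specified. Neither document commits to a between-arm estimate with an interval, an outcome SD or a centre ICC. On the Friedman route there would be no between-arm estimate at all.

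The matter is worth correcting because the hidden uncertainty is large: roughly ±0.75 to ±0.99 SD under the assumptions in step 3, against ±0.52 SD from an analysis blind to centre. The absence of the named outputs can be read directly from the documents. The widths are illustrations that rest on assumed ICCs. The gap can be closed from data already being collected, so it should be fixed but does not undermine the trial's conduct.

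**What to change.** Amend the SAP so that estimation is the main output for the outcomes.

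- **Scope:** the accelerometer primary outcome and the continuous secondary outcomes measured in both arms.
- **Main output at T1, T2 and T3:** the baseline-adjusted between-arm difference (or the difference in change from T0) with a 95% CI that respects the six randomised centres. Add the SD by arm and the T0-to-visit correlation.
- **Centre ICC:** report it with its interval for the primary outcome only. Plan any clustered main study over a range of ICC values, not the single estimate.
- **Exclusions:** make no between-arm comparison of Fitbit data, which come from the experimental arm alone. Summarise frailty status as proportions by arm.
- **P-values:** label them exploratory.

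The cost is new SAP wording and an analysis with a centre term, which the present plan lacks. No extra participants, visits or measurements are needed. The downside is that wide intervals become visible and the six-centre ICC will be very imprecise.

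### A K-S pre-test lets the outcome data choose between mean-based and rank-based analysis, so the quantity estimated is not fixed in advance

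*SAP*

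**What the plan says.** All of the relevant text is in the Statistical Analysis section of the SAP.

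- Normality check: "Normality assumptions for the variables will be examined by a K-S test".
- Between-group tests: "An independent sample Student's t-test or Mann-Whitney U test will be used to examine differences between the control and experimental groups".
- Effectiveness: "ANOVA will be used to measure the effectiveness of the intervention", followed by "If the data were non-normal, Friedman's test will be used instead".
- Within-group tests: "Post-hoc within-group comparisons will be done using paired t-tests or Wilcoxon's signed rank test, and Bonferroni adjustments will be made".
- Level: "A p-value of < 0.05 will be considered statistically significant".

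The switch is explicit for ANOVA and Friedman. For the other two pairs the SAP writes only an or, and the K-S test is the only selection rule it supplies. It does not say whether K-S is corrected for an estimated mean and SD, whether it is run on the pooled sample or per arm, or whether one decision per outcome binds all visits. The same section plans to adjust for baseline variables that differ between the groups.

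The protocol (Sample size) plans 60 participants from six centres randomised 1:1. It justifies 60 by a published recommendation for estimating an effect size on a continuous outcome. Outcomes are measured at baseline (T0) and at 1 week, 1 month and 3 months after the programme (T1 to T3; Instruments and Measures). The primary outcome is accelerometer-measured activity and sedentary time, with no SD or distribution given.

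**The concern.** A mean-based and a rank-based analysis answer different questions. If a test on the outcome data picks between them, the quantity to be reported for the primary outcome is unknown until the data are in. Three things then follow.

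- The decision may depend on an unstated software choice, because corrected and uncorrected K-S use very different critical values.
- For the t/Mann-Whitney and paired t/Wilcoxon steps, visits of one outcome may go to different tests, so their results would not be comparable.
- A rank result does not give the mean difference and SD that a pilot sized for effect-size estimation should hand to the main study. In the Friedman branch there is also no place for the planned covariates.

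**Working it through.** **The plan's own figure.** The 60 comes from a literature range of 60 to 100. There is no power, effect size or SD behind it, so there is nothing to reproduce. 60/2 = 30 per arm if centres recruit equally.

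**Inputs from the documents.** n = 30 (one arm) or 60 (pooled); three post-programme visits; level 0.05, taken to apply to K-S as well. T0 is left out of the splitting count because the SAP fixes an unpaired t test for continuous variables at baseline.

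**Assumptions.** Lognormal outcome with the same shape at each visit. Skewness = (exp(s²) + 2)·√(exp(s²) − 1). With s = 0.5: (1.284 + 2) × √0.284 = 1.75. Between-visit correlation is 0.7 on the log scale. Clustering and dropout are not simulated.

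**Method.** Monte Carlo simulation of K-S with estimated mean and SD. The uncorrected form uses the standard 5% critical values (0.242 at n=30, 0.172 at n=60). The corrected form uses values simulated under normality (0.159 and 0.114).

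| n | K-S variant | Rejects, log-SD 0.5 | T1–T3 split, log-SD 0.5 | Rejects, log-SD 0.3 to 0.8 |
|---|---|---|---|---|
| 30 | uncorrected | 4% | 11% | 0.4–23% |
| 30 | corrected | 48% | 64% | 22–83% |
| 60 | uncorrected | 17% | 36% | 2–67% |
| 60 | corrected | 79% | 45% | 40–99% |

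On the same shape at n=60, the unstated variant alone moves the rejection rate from 17% to 79%.

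**Dependence on shape.** Corrected test; the split column is pooled n=60 with correlation from 0.9 down to 0.5. These are separate runs, so a difference of a point or so from the table above is simulation error.

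| Shape (skewness) | Rejects, n=30 / n=60 | T1–T3 split |
|---|---|---|
| normal (0) | 5% / 5% | 14–15% |
| lognormal 0.6 | 13% / 20% | 35–48% |
| lognormal 0.95 | 22% / 39% | 49–68% |
| lognormal 1.3 | 35% / 62% | 48–69% |
| lognormal 1.75 | 49% / 78% | 36–49% |
| lognormal 2.9 | 74% / 96% | 9–11% |
| lognormal 6.2 | 93% / 99.9% | under 1% |

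Check on the normal row, with independent visits: 1 − 0.95³ − 0.05³ = 0.1425.

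The corrected test is near a coin toss for skewness of about 1.0 to 1.3 at n=60 and about 1.4 to 1.75 at n=30. Uncorrected, that band lies higher: at n=60 it rejects 51% at skewness 2.9.

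**Does the branch matter?** With 30 per arm and a 0.5 SD shift, two-sided t and Mann-Whitney tests disagree at 5% in 7% of trials (normal), 11% (skewness 0.95), 17% (1.75) and 28% (2.9). With no effect they disagree in 2–5%.

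**Type I error** (clustering ignored). The two-stage procedure gives 4.6–5.3%; either test fixed in advance gives 4.2–5.0%.

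**Arm effect as trigger.** With normal residuals and pooled n=60, K-S rejects in about 5% of samples for group differences up to 1.5 SD, 7% at 2 SD and 35% at 3 SD.

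**The case against.** The strongest reply is that this is a feasibility pilot seeking preliminary effects, that the pre-test does no harm to error control, and that the K-S sentence follows the baseline comparisons and may have been meant only for them. The first two parts stand. The third does not remove the problem, because the condition "If the data were non-normal" has no other test by which to be judged.

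A reader might also infer more than the documents support.

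- *That T1, T2 and T3 can go to different branches in the effectiveness analysis.* They cannot if ANOVA and Friedman each take the whole repeated series, which is the natural reading of a repeated-measures design. Splitting is confined to the t/Mann-Whitney and paired t/Wilcoxon steps, where the K-S trigger is itself inferred.
- *That the choice is close to arbitrary.* This holds only for intermediate skew. Under the corrected test, near-normal data stay mean-based about 95% of the time, and at n=60 data with skewness of about 2.9 or more go to ranks in 96% or more of samples. The documents do not say which case applies.
- *That a real arm effect would trip the switch, because raw values rather than residuals are tested.* The SAP says only that variables are tested, and a difference of up to 1.5 SD leaves the rejection rate near 5%.
- *That every rank branch loses the covariates.* A t-test carries none either. The loss is specific to moving from ANOVA to Friedman.

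**Conclusion.** The point holds in a limited form. The SAP makes the analysis depend on a K-S test, explicitly for ANOVA versus Friedman and by implication for the other two pairs, without stating the variant, the unit tested or a rule across visits. Under the assumed lognormal (log-SD 0.5, correlation 0.7), rejection ranges from about 4% to 79% across sample unit and variant, and T1 to T3 split in about 11% to 64% of trials. These sizes rest on an assumed shape and ignore clustering and dropout. The splitting figures are for values at each visit, not for paired differences.

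The consequence is not a false-positive problem. It is that the data choose between a mean difference and a rank comparison. The rank branch does not deliver the effect size on which the sample size is justified. Friedman's test, being a within-subject test over time, has no group factor and no route for the planned baseline adjustment.

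**What to change.** Delete the K-S rule and the Friedman switch. For each continuous outcome, name one mean-based analysis on one named scale, used at every visit, that compares the groups and can carry the baseline covariates; a repeated-measures model with group, visit and their interaction would do. Choose the scale now rather than leaving alternatives open. If a log scale is named, state how zero minutes are handled and that results are reported as ratios. Check residuals graphically. Report one pre-stated rank-based or centre-level permutation analysis as a sensitivity analysis only.

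Cost: SAP wording. With one method per outcome, splitting between visits is 0% by construction. Some efficiency is lost if an outcome proves strongly skewed on the chosen scale. If the permutation test is used, six centres split 3:3 give C(6,3) = 20 allocations, so its two-sided p-value cannot fall below 2/20 = 0.10. It can never reach the SAP's 0.05 and should be labelled descriptive.
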